### Open-Label Period

#### **10.4 Visit 4 – Day 56 (visit window +/- 4 days), Open-Label Week 4**

1. Administer PRO questionnaires (CFRSD-CRISS and CFQ-R).
2. Review subject diary.
3. Perform pill count on returned azithromycin.
4. Record any AEs.
5. Record changes to concomitant medications. If a new IV, oral or inhaled antibiotic was prescribed, ensure that a Signs and Symptoms form was completed.
6. Perform abbreviated physical examination.
7. Measure and record height and weight.
8. Obtain and record vital signs.
9. Perform and record spirometry.
10. If able to expectorate sputum, collect expectorated sputum.

11. Provide subject diary.
12. Instruct subject to bring the azithromycin bottle, any remaining tablets, and diary to Visit 5.
13. Review inhaled tobramycin schedule and remind subject to take TISP between Visits 4 and 5.
14. Schedule subject for Visit 5.

### **10.5 Visit 5 - Day 84 (visit window +/- 4 days), Open-Label Week 8**

1. Administer PRO questionnaires (CFRSD-CRISS and CFQ-R)
2. Review subject diary.
3. Perform pill count on returned azithromycin.
4. Record TISP use.
5. Record any AEs.
6. Record changes to concomitant medications. If a new IV, oral or inhaled antibiotic was prescribed, ensure that a Signs and Symptoms form was completed.
7. Perform abbreviated physical examination.
8. Measure and record height and weight.
9. Obtain and record vital signs.
10. Perform and record spirometry.
11. Obtain resting ECG.
12. If able to expectorate sputum, collect expectorated sputum.
13. Instruct subject that study participation is complete and to use medications according to instructions from clinical care providers.

### **10.6 Unscheduled\* or Early Discontinuation of Study Drug or Study Participation Visit**

\*An Unscheduled Visit may be conducted as a study visit when, in the opinion of the site investigator, safety follow up is required as a result of a possible study-related procedure or study drug-related event.

1. Administer PRO questionnaires (CFRSD-CRISS and CFQ-R).
2. Review subject diary.
3. Perform pill count on returned study drug (if during randomized period) or azithromycin (if during open-label period).
4. Record any AEs.
5. Record changes to concomitant medications. If a new IV, oral or inhaled antibiotic was prescribed, ensure that a Signs and Symptoms form was completed.
6. Perform complete physical examination.

7. Measure and record height and weight.
8. Obtain and record vital signs.
9. Perform and record spirometry.
10. Obtain resting ECG, if appropriate (see footnote b in Table for Schedule of Events).
11. If able to expectorate sputum, collect expectorated sputum.

## 11 ADVERSE EXPERIENCE REPORTING AND DOCUMENTATION

### 11.1 Adverse Events

An AE is any untoward medical occurrence in a clinical investigation of a patient administered a pharmaceutical product and that does not necessarily have a causal relationship with the treatment. An AE is therefore any unfavorable and unintended sign (including an abnormal laboratory finding), symptom or disease temporally associated with the administration of an investigational product, whether or not related to that investigational product. An unexpected AE is one of a type not identified in nature, severity, or frequency in the current Prescribing or Product Information or of greater severity or frequency than expected based on the information in the Prescribing or Product Information.

The site investigator will probe, via discussion with the subject, for the occurrence of AEs during each subject visit and record the information in the site's source documents. Adverse events will be recorded in the subject CRF.

#### AE Severity

The National Cancer Institute's Common Terminology Criteria for Adverse Events (CTCAE) Version 4.0, as modified for CF, should be used to assess and grade AE severity, including laboratory abnormalities judged to be clinically significant. The modified criteria can be found in the Study Reference Binder. If the experience is not covered in the modified criteria, the guidelines shown in Table 1 below should be used to grade severity. It should be pointed out that the term "severe" is a measure of intensity and that a severe AE is not necessarily serious.

**Table 1. AE Severity Grading**

Severity (Toxicity Grade)	Description
Mild (1)	Mild; asymptomatic or mild symptoms; clinical or diagnostic observations only; intervention not indicated
Moderate (2)	Moderate; minimal, local or noninvasive intervention indicated; limiting age-appropriate Instrumental activities of daily living (e.g., preparing meals, using the telephone, managing money)
Severe (3)	Severe or medically significant but not immediately life-threatening; hospitalization or prolongation of hospitalization indicated; disabling; limiting self-care activities of daily living (e.g., bathing, dressing, feeding self, using toilet, taking medications)
Life-threatening (4)	Life-threatening consequences; urgent intervention indicated
Death (5)	Death related to AE

### AE Relationship to Study Drug

The relationship of an AE to the study drug (azithromycin or placebo for the randomized period, azithromycin for the open-label period) should be assessed using the following the guidelines in Table 2.

**Table 2. AE Relationship to Study Drug**

Relationship to Drug	Comment
Definitely	Previously known toxicity of agent; or an event that follows a reasonable temporal sequence from administration of the drug; that follows a known or expected response pattern to the suspected drug; that is confirmed by stopping or reducing the dosage of the drug; and that is not explained by any other reasonable hypothesis.
Probably	An event that follows a reasonable temporal sequence from administration of the drug; that follows a known or expected response pattern to the suspected drug; that is confirmed by stopping or reducing the dosage of the drug; and that is unlikely to be explained by the known characteristics of the subject's clinical state or by other interventions.
Possibly	An event that follows a reasonable temporal sequence from administration of the drug; that follows a known or expected response pattern to that suspected drug; but that could readily have been produced by a number of other factors.
Unrelated	An event that can be determined with certainty to have no relationship to the study drug.

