## 2.1 Risk / Benefit Assessment

No experimental or new medications are being introduced to subjects during this study. Removal of chronic azithromycin may decrease lung function or increase the rate of pulmonary exacerbation, based on prior studies of azithromycin in similar patients. Our preliminary data does not support this concern and suggest that removing azithromycin may be protective in the majority of subjects also using inhaled tobramycin. This includes better clinical outcomes in lung function (FEV1), patient reported quality of life, and time to need additional antibiotics. However, a withdrawal study of either medication has never been reported and our preliminary data on lung function may not fully predict the risk of pulmonary exacerbation. Subjects experiencing a pulmonary exacerbation will be treated but will not be removed from the study.

Identifying an undesirable drug-drug interaction pertinent to over 50% of US patients with CF has clear and important safety and efficacy implications. Given that both of these medications benefit from strong support in US consensus guidelines, answering this question is a high priority.

Recent reports raise concern about potential proarrhythmic cardiotoxicity with oral azithromycin treatment in non-CF populations. Patients with CF account for a significant portion of chronic azithromycin use in the US and cardiac arrhythmias have not been linked to this therapy. Similarly, the relative risk of cardiovascular death attributable to azithromycin was reported as <1 per 100,000 antibiotic courses in low risk patients. There are approximately 30,000 CF patients in the entire US, and a repeat study found no increased risk in younger, lower risk adult populations. However, this study provides an opportunity to analyze electrocardiograms (ECGs), focusing on any effect on QTc interval, in a group of CF subjects both on and off of azithromycin.

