## 8.3 Unblinding Procedures

During the study, the blind may be broken for individual subjects in emergencies when knowledge of the subject's treatment group is necessary for further patient management or when the event meets the FDA expedited reporting requirements as a suspected adverse reaction that is serious and unexpected (21 CFR 312.32(c)(1)(i)). In those cases, knowledge of the treatment received is necessary for interpreting the event. Individual SAEs that are unexpected, deemed related to study drug, and confirmed by the Medical Monitor will be forwarded to the DSMB Chair within 7 business days. Additional information or data summaries may also be requested by the DSMB at this time.

If the blind is broken and the subject is on study drug, a Safety Report will be sent to all participating investigators. Emergency unblinding procedures are provided in the Study Manual. Refer to protocol section 11.2.1 Serious Adverse Experience Reporting.

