**9.1.15 Adverse Events**

Information regarding occurrence of AEs will be captured throughout each subject's study participation, starting after the first dose of study drug and ending once the subject has

terminated from the study. Duration (start and stop dates), grade, seriousness, outcome, treatment and relation to study participation will be recorded on the CRF.

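### No category in the protocol's causality table fits a serious adverse event of a new type, so the 7-business-day notice to the DSMB Chair may not be triggered for it

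*Protocol*

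**What the plan says.** Protocol section 11.1 asks sites to rate each adverse event against the study drug and offers Table 2 as guidelines. The table has four rows.

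- *Possibly*: plausible timing and an event "that follows a known or expected response pattern to that suspected drug", although other factors could readily explain it.
- *Probably*: among other conditions, an event "that follows a known or expected response pattern to the suspected drug".
- *Definitely*: opens with "Previously known toxicity of agent; or an event that follows a reasonable temporal sequence from administration of the drug" and then adds the same pattern condition.
- *Unrelated*: "An event that can be determined with certainty to have no relationship to the study drug".

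The same section defines the term unexpected: "An unexpected AE is one of a type not identified in nature, severity, or frequency in the current Prescribing or Product Information". An event of known type also counts if it is more severe or more frequent than that information leads one to expect.

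Section 8.3 joins the two ratings and sets a limit of 7 business days: "Individual SAEs that are unexpected, deemed related to study drug, and confirmed by the Medical Monitor will be forwarded to the DSMB Chair".

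Section 9.1.15 describes the causality field differently: "relation to study participation will be recorded on the CRF". The tabulations in protocol section 15.4 and SAP A.4 use relationship to study drug.

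**The concern.** A causality scale should give every event a place, and above all an event nobody has seen with the drug before. Here the related rows look for something already known or expected, and the unrelated row asks for a certainty that is rarely available. Section 8.3 meanwhile reserves its rapid notice for SAEs that are both unexpected and related. For events unexpected because of their type, the scale and the notice rule pull against each other.

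At stake are the rapid notice to the DSMB Chair and the consistency of the relatedness tables. With about 40 sites and no other causality standard in the documents, investigators could place the same kind of event in different rows.

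**Working it through.** No arithmetic applies. The check takes one event through the table and then through section 8.3.

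**Test event.** An SAE of a type absent from the product information, with plausible timing, no response pattern known for azithromycin, and no other cause established.

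| Row of Table 2 | Condition that decides | Does the test event meet it? |
|---|---|---|
| *Definitely*, first limb | Toxicity already known | No |
| *Definitely*, second limb | Known or expected pattern | No |
| *Probably* | Known or expected pattern | No |
| *Possibly* | Known or expected pattern | No |
| *Unrelated* | Certainty of no relationship | No, since no other cause is established |

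The event meets no row. The result is a gap, which leaves the rating to the individual investigator.

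**Section 8.3.** The notice to the DSMB Chair has three conditions.

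1. Unexpected: met, because the type is not in the product information.
2. Deemed related to study drug: not supported by any row of Table 2. It is met only if the investigator goes outside the table.
3. Confirmed by the Medical Monitor: follows only if the second is met.

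**What is not affected.**

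- An SAE of known type that is unexpected in severity or frequency can satisfy both Table 2 and section 8.3.
- The FDA trigger in section 8.3 cites the regulation and does not refer to Table 2.
- Section 11.2.1 has every SAE, related or not, sent to the TDNCC within one business day of the site learning of it.
- Section 11.3 has the Medical Monitoring Group review SAEs and contact the DSMB on a set schedule and additionally when warranted.
- Section 14 has the DSMB monitor SAEs continuously, and SAP 1.2 adds quarterly SAE tables by treatment group.

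**Which relationship is recorded.** Section 9.1.15 names study participation. Section 11.1, section 15.4 and SAP A.4 name study drug. These are different questions: an event can arise from a study procedure or from the design without being a response to the capsule. The documents do not say whether one field or two are meant.

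**The case against.** The strongest reply is that Table 2 is only guidance. Section 11.1 says that relationship should be assessed with it, and section 8.3 does not cite it. An investigator who suspects the drug may still call the event related, and the Medical Monitor may agree. This stands, and it limits the conclusion to what may happen under a literal reading. It does not remove the gap, because no other standard is given.

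A second reply is that the word expected is used in two senses. Section 11.1 ties unexpected to the product information, whereas the pattern in Table 2 is not tied to any source. An unlisted event could still follow a pattern recognised for the drug and so qualify as *Possibly*. This also stands. The gap concerns events that are both unlisted and without a recognised pattern.

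A third reply is that the safety net is wide and that section 2.1 says no new medications are introduced, so new-type SAEs should be uncommon. This is fair, and it makes the point one about a rapid notice and a rating. SAEs are not lost.

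A reader might also infer that the table hides harm from stopping azithromycin in the placebo arm, since section 2.1 warns: "Removal of chronic azithromycin may decrease lung function or increase the rate of pulmonary exacerbation". The documents do not support adding that here. Such events fall outside Table 2 mainly because it rates the drug being given. Section 2.1 anticipates them, and whether they would count as unexpected depends on product information that is not supplied. They are also assessed by randomised comparison of exacerbations, hospitalisations and antibiotic use (protocol section 15.4, SAP A.6) and by SAE tables by arm.

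**Conclusion.** The concern holds in a limited form. The four categories of Table 2 are not exhaustive: an SAE of a new type with plausible timing fits none of them. Applied literally, the table may keep such an event from being deemed related, and the 7-business-day notice to the DSMB Chair may then not be triggered. Separately, section 9.1.15 disagrees with section 11.1, section 15.4 and SAP A.4 on which relationship is rated.

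A reader might go further and infer that a new-type SAE is barred from a related rating, or that expedited reporting cannot work. Neither follows. The event is left unclassified, the table is guidance, and the FDA trigger rests on the regulation.

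The size cannot be put as a number. The 75% of US inhaled-tobramycin patients also prescribed azithromycin (protocol section 1) describes drug use and gives no count of misrated SAEs. The conclusion assumes that sites follow Table 2 as written and that the Study Manual and DSMB charter, which were not available, contain no overriding causality rule.

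**What to change.** In Table 2, remove the known-or-expected-pattern condition from *Possibly*, so that plausible timing and a relationship that cannot be excluded are enough. Under *Unrelated*, replace the certainty test with a standard that another cause is more likely. Word the two rows together so that every event falls into exactly one category and the scale agrees with section 8.3.

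Reconcile section 9.1.15 with section 11.1, section 15.4 and SAP A.4. If both relation to study drug and relation to study participation are intended, record them as separate CRF items and tabulate both. Do not let relation to participation widen the triggers in section 8.3, because that section also governs individual unblinding and Safety Reports to all investigators.

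The cost is a protocol wording change, a memo to sites, and a CRF item and table if both relationships are kept. The downside is somewhat more events rated possibly related.

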### 11.2 Serious Adverse Experiences (SAE)

An SAE is defined as any AE occurring at any dose that results in any of the following outcomes:

- death
- a life-threatening adverse experience
- inpatient hospitalization or prolongation of existing hospitalization
- a persistent or significant disability/incapacity
- a congenital anomaly/birth defect

Other important medical events may also be considered an SAE when, based on appropriate medical judgment, they jeopardize the subject or require intervention to prevent one of the outcomes listed.

#### 11.2.1 Serious Adverse Experience Reporting

Study sites will document all SAEs that occur (whether or not related to study drug) on an SAE Report Form. The collection period for all SAEs will begin after informed consent is obtained and end after procedures for the final study visit have been completed.

All SAE Report Forms will be reviewed by the site investigator and sent to the TDNCC within one business day of the site learning of the event. Sites will send the SAE report by either:

- Email (scanned copy) to: [[contact]](mailto:[contact])
- TDNCC SAE [contact]

The site will notify the Medical Monitor of additional information or follow-up to an initial SAE Report as soon as relevant information is available. The Medical Monitor may request additional information related to the SAE. Follow-up information is reported on an SAE Report Form.

In accordance with the standard operating procedures and policies of the local Institutional Review Board (IRB), the site investigator will report SAEs to the IRB.

### 11.3 Medical Monitoring

The TDNCC Medical Monitoring Group should be contacted directly at this number to report medical concerns or questions regarding safety.

- [contact]

The TDNCC Medical Monitoring Group will serve as the independent Medical Monitors for this study. AEs and SAEs will be collected and organized by the TDNCC and provided to the TDNCC Medical Monitoring Group for review in a timely manner. The TDNCC Medical Monitoring Group will communicate with the independent DSMB at a predetermined schedule, and additionally as warranted.

## 12 DISCONTINUATION AND REPLACEMENT OF SUBJECTS

### 12.1 Early Permanent Discontinuation of Study Treatment

A subject may be permanently discontinued from study treatment at any time if the subject, the investigator, or the Sponsor-Investigator feels that it is not in the subject's best interest to continue. The following is a list of possible reasons for early permanent discontinuation of study treatment:

- Subject or subject's legal representative decision
- Adverse event, including pulmonary exacerbation
- Protocol violation
- Death

If a subject is discontinued from treatment due to an AE, the subject will be followed and treated by the site investigator until the abnormal parameter or symptom has resolved or stabilized.

All subjects who permanently discontinue study treatment early should come in for an early discontinuation of study treatment visit as soon as possible (see Appendix 1) and then should be encouraged to complete all remaining scheduled visits and procedures.

Refer to Section 8.6.2 for temporary discontinuation of study drug.

### 12.2 Early Withdrawal of Subjects from the Study

All subjects are free to withdraw from participation at any time, for any reason, specified or unspecified, and without prejudice. This may include subjects who withdraw from study

treatment early and who decline to continue to come in for remaining follow-up visits or it may include subjects who completed treatment and decline to come in for remaining follow up visits.

Reasonable attempts will be made by the investigator to provide a reason for early subject withdrawals. The reason for the subject's early withdrawal from the study will be specified in the subject's source documents. Subjects who withdraw early from the study should be encouraged to come in for a final early study withdrawal visit (and the procedures to be followed would include those for an early discontinuation of study drug visit – see Appendix 1).

### 12.3 Replacement of Subjects

Subjects who withdraw from the study will not be replaced.

## 13 PROTOCOL VIOLATIONS

A protocol violation occurs when the subject, investigator, or the Sponsor fails to adhere to significant protocol requirements affecting the inclusion, exclusion, subject safety and primary endpoint criteria. Protocol violations for this study include, but are not limited to, the following:

- Failure to meet eligibility criteria
- Use of a prohibited concomitant medication. This includes the use of conditionally allowed medications without meeting the criteria to use these medications (e.g. Temporarily stopping study drug or open-label azithromycin).
- Failure to obtain spirometry at Visits 1-3

Failure to comply with Good Clinical Practice (GCP) guidelines will also result in a protocol violation. The Sponsor-Investigator will determine if a protocol violation should result in early discontinuation of study treatment for a subject.

When a protocol violation occurs, it will be discussed with the investigator and a Protocol Violation Form detailing the violation will be generated. This form will be signed by a Sponsor representative and the site investigator. A copy of the form will be filed in the site's regulatory binder and in the Sponsor's files. The site will report the violation to their IRB in accordance with their IRB reporting requirements.

## 14 DATA SAFETY MONITORING

A Data Safety Monitoring Board (DSMB) will review comprehensive interim enrollment, safety, and efficacy data reports when approximately 50% and 75% of patients have completed the randomized period of the study. Regular reporting frequency to the DSMB is detailed in the DSMB charter. *A priori* interim stopping rules for futility and efficacy/harm with respect to the primary endpoint are outlined in the DSMB charter. SAEs will be monitored by the committee on an ongoing basis throughout the study. Further details are included in the DSMB charter.

## 15 STATISTICAL METHODS AND CONSIDERATIONS

A detailed statistical analysis plan will be written that will describe all analyses that will be generated for this study. All analyses will be performed using SAS® (SAS Institute, Inc., Cary, NC, USA) or R (R Foundation for Statistical Computing, Vienna, Austria).

